13.1. Risks

Participation in this study does not include any risk for the participants as the study does not test any drugs and participation in this study does not interfere with the treatment/care participants may receive at their regular HIV clinic. Pregnant women may participate in the study, as no interference with their treatment or pregnancy in any way will take place. Within the HIV service clear pathways for the management of medical complications exist and all issues will follow these pre-defined pathways.

13.2. Benefits

There are no direct benefits to the participants. However, the benefit of conducting observational research includes advancing scientific understanding of how LA ART is being implemented in the UK; this knowledge may guide treatment recommendations to the benefit of people living with HIV.

14. Withdrawal from study

Withdrawal from the study may be required if the participant withdraws consent as they no longer wish to participate. The decision to withdraw and the reason will be documented in the eCRF. The participant will be informed that data and samples collected up to that point will be retained for the purposes of the study, with their permission.

If a participant is lost to follow-up they can remain in the cohort and their missed visits will be documented in the eCRF. It is important to allow data collection on these individuals in case they return at a later date as describing their outcomes is of interest.

If an individual transfers out to another clinic it may not be possible to collect their routine clinic data (e.g. viral load data) however they can still complete questionnaires and therefore can remain in the cohort. The reason the laboratory data is missing will be recorded in the eCRF.

15. Fthical Considerations

The investigator(s) will ensure that this study is conducted in full conformity with the 7^{th} revision of the 1964 Declaration of Helsinki. The study will be conducted in accordance with the guidelines laid down by the International Conference on Harmonisation for Good Clinical Practice (ICH GCP E6 guidelines and Addendum ICH GCP E6 (R2)).

15.1. Ethics committee approval

Prior to the enrolment of participants, the Sponsor's research ethics committee (REC) and the Health Regulatory Authority (HRA) must provide written approval of the conduct of the study at named sites, the protocol and any amendments, the Participant Information Sheets and Informed Consent Forms, any other written information that will be provided to the participants, any advertisements that will be used and details of any subject compensation.

Any proposed amendments to the protocol or informed consent forms must be submitted to the REC for approval and may be implemented only after REC approval has been obtained. The amended protocol will be sent to participating sites for local approval to be granted and the approved version will be shared with all staff involved in the study.

15.1.1. Annual progress reports

The REC will be sent annual safety reports on the anniversary of each REC approval until the end of study, in order to facilitate their continuing review of the study (reference. ICH GCP E6 Section 3.1.4). The REC will be informed of the End of Study, as defined in this protocol, within the required timelines.

15.1.2. Health Research Authority approval

HRA approval will be obtained prior to starting the study. Each participating site will confirm capacity and capability prior to commencing. The HRA and all participating sites also need to be notified of all protocol amendments to categorise the amendment and assess whether the amendment affects the institutional approval for each site.

15.1.3. Non-compliance with the Protocol

Deviations from research protocols and GCP occur commonly, the majority of these instances are technical deviations that do not result in harm to the participants or significantly affect the scientific value of the reported results of the trial. Protocol deviations (PD) or violations (PV) should be documented in the deviation case report form in REDCap in order for corrective and preventative actions to be taken.

The Investigators will review all PDs and PVs. PVs will also be reported to the Sponsor. It is the responsibility of the Sponsor to assess the impact of the breach on the scientific value of the and an assessment of whether the PV constitutes a serious breach will be made.

15.1.4. Serious Breach

A serious breach is defined as a breach of the principles/conditions of GCP, or of the trial protocol, that affect to a significant degree the safety of trial participants or the scientific value of the trial. The Sponsor should be notified within 24 hours of identification of a serious breach. The judgement on whether a breach is likely to have a significant impact on the scientific value of the trial depends on a variety of factors e.g. the type and extent of the data affected by the breach, the overall contribution of the data to key analysis parameters, the impact of excluding the data from the analysis etc. Examples of serious breach:

- Breach of GCP or protocol leading to the death, hospitalisation or permanent disability of a participant
- Proof of fraud relating to clinical trial records or data
- Persistent or systematic non-compliance with GCP or protocol that has a significant impact on the integrity of trial participants in the UK
- Failure to comply with safety reporting requirements.

The Sponsor will notify REC within 7 days of becoming aware of a serious breach.

15.1.5. Insurance and Indemnity

The Sponsor has civil liability insurance, as well as negligent harm and non-negligent harm insurance policies which apply to this study.

15.1.6. Informed consent process

Informed consent will be obtained from all participants using REC approved Participant Information Sheet(s) (PIS) and Informed Consent Form(s) (ICF).

The participant will be informed about the rationale and requirements of the study via the electronic PIS. Or where there are any reading difficulties, or if the potential participant has questions, the PIS can be downloaded and printed and an in-person consent process with the research team can be completed. Potential participants will be given an adequate amount of time to consider their participation in the study. If they decide to participate in the study they will be asked to sign the ICF on-line, which will then be countersigned by site Investigator online. The participant will be emailed a copy of the signed ICF, another copy will be downloaded and filed in the participant's research records at the site.

The right of the participant to refuse to participate without giving reasons must be respected. All participants are free to withdraw at any time from the study without giving reasons and without prejudicing further treatment.

15.1.7. Confidentiality

The Investigators must ensure that the participant's confidentiality is maintained in accordance with Good Clinical Practice (GCP) Guidelines. Study participants are de-identified and anonymised with a Unique Patient Identifier (PID). A de-coding list is held in a safe location by the individual site and it is the responsibility of cohort PI/local study staff to secure this. All data shared will contain the PID number and no unique person identifiers. On the eCRF or other documents submitted to the Sponsor, the participant will be identified by a participant ID number only. Only the Central Data Manager will have access to the participant ICF where the name is evident.

The Investigator shall permit direct access to participants' records and source documents for the purposes of monitoring, auditing, or inspection by the Sponsor, authorised representatives of the Sponsor and REC.

15.1.8. Data Protection

The investigator will preserve the confidentiality of all participants taking part in the study, which will be conducted in accordance with the General Data Protection Regulation (GDPR). The investigators and study site staff will comply with the requirements of the Data Protection Act 2018 concerning the collection, storage, processing and disclosure of personal information and will uphold the Act's core principles.

15.1.9. Remuneration

Participants are not remunerated for joining the cohort study. However, the time participants spend on a questionnaire, or for those who undergo an in-depth interview, will be remunerated with a £20 shopping voucher.

The participating research site is reimbursed for completed deliverables e.g. enrolment, eCRFs submitted in REDCap, completion of clinic registry for the adoption cascade.

16. Data Management

The research tools and eCRFs are in English. Generic names for concomitant medications should be recorded in the CRF wherever possible. All written material to be used by subjects must use vocabulary that is clearly understood, and be in the language appropriate for the study site.

16.1. Source data

Source documents include original documents related to the study data (e.g. patient medical records which can be paper-based or electronic). Adequate source documentation must be maintained at participating sites to allow reliable verification and validation of the study data.

For questionnaires that are administered directly on-line the eCRF is the source document.

16.2. Data collection and Database

Study data will be collected on an electronic case report forms (eCRFs). The principal means of data collection from participant visits will be Electronic Data Capture (EDC) using the REDCap database. Data are entered into REDCap system by trained site personnel. Data entered by the site team will include demographics, medical history, HIV treatment history, blood test results, protocol deviations etc.

The participants will be sent on-line REDCap questionnaires at month 0, 6 and 12 and by answering the questions will be directly entering data. If the participant is unable to directly enter data on the REDCap questionnaires the data from a paper-based questionnaire can be entered into REDCap on behalf of the participant by a member of the study team.

All changes made following initial submission of data will have an electronic audit trail with a date. Specific instructions and further details will be outlined in the study specific eCRF completion manual.

16.3. Data storage and archiving

The investigator must retain essential documents until notified by the Sponsor, and for at least ten (10) years after study completion. Participant files and other source data (including copies of protocols, CRFs, original reports of test results, correspondence, records of informed consent, and other documents pertaining to the conduct of the study) must be retained. Documents should be stored in such a way that they can be accessed/data retrieved at a later date. Consideration should be given to security and environmental risks.

No study document will be destroyed without prior written agreement between the Sponsor and the investigator. Should the investigator wish to assign the study records to another party or move them to another location, written agreement must be obtained from the Sponsor. All data collected during the study will be stored in the UK.

Data is held securely by the Sponsor for at least 10 years on a password-protected electronic folder in the University of Sussex hosting service (One Drive).

16.4. Data sharing

We will be proactive in ensuring that this valuable data is used to its full potential. The Study Management Group (SMG) will welcome proposals for collaborations from other academic groups as well as the study funders. Those potentially interested should submit a proposal to the SMG containing information about the project, analysis plan and data requirements. Proposals will then be discussed by the SMG and will be approved if it is felt to be scientifically valid with appropriate methodology. Any request for sharing the study dataset must be approved by the SMG.

17. Statistical Considerations

As this is primarily a descriptive study no formal power calculation is required. The inclusion of a group of people receiving oral ART is to give an indication of the outcomes that would be seen had the participant not switched to LA CAB+RPV, but it is not our intention at this stage to formally compare groups due to the expected differences in characteristics of the two groups. Across all study sites the aim is to recruit a minimum of 150 adults receiving LA CAB+RPV into the prospective cohort study and ~50 adults who remain on oral ART as the comparator population. Around 20-30 participants will participate in the qualitative study.

Detailed description of the statistical analyses, any deviation from the protocol, and assumptions employed will be presented in a detailed Statistical Analysis Plan (SAP) that will be prepared prior to database closure and initiation of any statistical analyses below.

The demographic, clinical and treatment characteristics of all participants (age, BMI, race/ethnicity, co-morbidities, ART history) will be presented as summary statistics (mean,

median, standard deviation, IQR, maximum and minimum for continuous measurements, and numbers and proportions for categorical measurements), stratified by group (LA CAB+RPV, oral ART).

We anticipate most participants will have virological suppression at baseline; in such participants the proportion of participants with sustained virologic suppression at 6 and 12 months will be described. For those who are not virologically suppressed at enrolment, changes in viral load will be described.

Amongst those with available longitudinal CD4 count data, renal data (creatinine / eGFR) and lipid data (total cholesterol, total:HDL cholesterol ratio and triglycerides) the mean change from baseline in the LA CAB+RPV group and the oral group will be described.

The number and proportion of participants who discontinue LA CAB+RPV and the reason for discontinuation will be described.

The 'end of study' is the point at which last participant final visit individual data has been entered into the electronic data capture system and all the qualitative work has been completed. Thereafter, the 'end of study' the close out visit will be performed. The study will only be considered 'closed' when all participants have completed their final study visit, all assessments completed, all the data have been entered into the database and all data queries resolved, close out visit conducted, the database locked and data analysis performed and reports written.

18. Study Management and Oversight

The study has undergone independent peer review at the Protocol Review Panel at University of Sussex.

The study will be managed via the Brighton and Sussex Medical School Department of Global Health and Infection at the University of Sussex. The study management group (SMG) consisting of the Chief Investigators, Co-Investigators, Study Manager, Data Manager will be responsible for the day-to-day conduct of the study and will troubleshoot any operational issues.

As this is a low-risk non-interventional protocol, there is no requirement for a data safety monitoring committee for this study. University of Sussex safeguarding policies will be followed https://www.sussex.ac.uk/safeguarding/.

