Around 20-30 participants will participate in the nested
qualitative study.
Around 30 healthcare workers will contribute data through focus
group discussions and questionnaires

7. Background and Rationale

The long-acting injectable antiretroviral therapy regimen of cabotegravir and rilpivirine (LA CAB+RPV) given 2-monthly is a remarkable, promising and widely welcomed paradigm shift in HIV treatment [1-4]. The regimen was recently approved by the National Institute for Clinical Excellence (NICE) and roll out is underway in the United Kingdom (UK) National Health Service (NHS) [5]. Current trial data suggest it is an efficacious regimen and is well-liked by the majority of trial participants [1-4][6]. There are multiple advantages over traditional oral antiretroviral therapy, such as it being less user-dependent, removing the burden of daily pill-taking, and being more easily concealed, reducing concerns around stigma [7].

Outside of trials, to date LA CAB+RPV has only been used in select circumstances on compassionate grounds in small numbers of individuals unable to take oral therapy. Therefore, there are currently no real-world data on the implementation strategies planned in different clinical settings, the feasibility and acceptability of LA CAB+RPV to patients and clinicians, nor clinical outcomes with the regimen outside of clinical trial settings [8, 9]. HIV services throughout the UK are currently planning and executing local roll out of LA ART but it is not yet known how this will be individualised based on patient needs and service capacity. Clinical trial data does not address the practical needs of the stakeholders responsible for introducing the intervention and more data are urgently needed in this area. This is especially pertinent to LA CAB+RPV considering it requires increased frequency of visits and HIV viral load (VL) monitoring, adequately trained clinical staff, robust injection appointment management systems, oral bridging in events of delayed injections and all this must be incorporated into existing clinic work streams and human resources [10].

The British HIV Association (BHIVA) have released guidance on eligibility for LA ART based on the following nine criteria [9]:

- 1. significant need for injectable antiretroviral therapy;
- 2. viral suppression for at least 6 months;
- 3. no known or suspected NNRTI or INSTI resistance;

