ACCEPTIBILITY 2a. To explore the acceptability of LA CAB+RPV amongst PLWH and health care workers delivering the regimen through a participant questionnaire, healthcare practitioner questionnaire and qualitative research. 2b. To compare patient-reported outcomes including quality of life, treatment satisfaction and treatment preference in those on LA CAB+RPV compared to those who remain on oral ART (demographically similar but not eligible for LA ART)	 a. The acceptability and experiences of the regimen amongst participants (PLWH) and healthcare workers delivering LA CAB+RPV through outcomes in the participant and HCP questionnaires b. The patient reported outcomes will be described through: i. Outcomes in the participant questionnaire and treatment preference in those switched to LA CAB+RPV ii. HIV-related quality of life - HIVPROM (11) 	
FEASIBILITY	a. Outcomes in the healthcare worker and participant questionnaires	

	CORAL
3a. To describe feasibility through outcomes in the participant and healthcare practitioner questionnaires 3b. To explore barriers and facilitators to effective implementation	b. Experiences, barriers and facilitators at both the individual and service level from qualitative work
FIDELITY	 a. Proportion of injections delivered within the visit window b. Number of oral bridging courses per patient per year c. Fidelity to 2-monthly HIV viral load monitoring (+/- 2 weeks of target date)
Effectiveness outcomes	
EFFECTIVENESS 5a. To characterise the UK-wide population who are switched to LA CAB+RPV and indications for switch 5b. To describe virological and clinical outcomes at one year of therapy in those on LA CAB+RPV and in those remaining on oral ART (demographically similar but not eligible for LA ART)	 a. Proportion of those who begin LA CAB+RPV who remain virologically suppressed at 12 months (by FDA snapshot algorithm and intention to treat approach), and the proportion of those on oral ART who remain virologically suppressed at 12 months after the baseline date b. Proportion of each group who have experienced virological failure at 12 months c. HIV-related medical events at 12 months d. Change in CD4 count from baseline to month 12 (where available) e. Change in renal function (estimated glomerular filtration rate, eGFR) from baseline to month 12

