11.2.1. Inclusion criteria for observational study using routinely collected clinic data

- 1. Understands the participant information and study requirements and has capacity to consent.
- 2. Willing to comply with study procedures
- 3. Age 16 years or above
- 4. Is a member of one of the following groups:
 - LA group PLWH who have been recently switched (within the prior 6 months) or are prospectively switched to LA CAB+RPV during the enrolment period. This includes those who have received LA CAB+RPV outside of BHIVA criteria or on compassionate grounds.
 - Oral ART group PLWH who are demographically similar but not eligible for LA CAB+RPV according to BHIVA eligibility criteria and who continue oral ART within the study period (e.g. those who are HBVcoreAb+ or who have an underlying drug resistance mutation that precludes use of LA CAB+RPV). Intervention group to oral group will be matched 3:1 by calendar period and other key variables where possible.

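### Section 17 gives CD4 change as one mean per treatment group, so each mean can mix recovery in participants viraemic at baseline with change in those already suppressed

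*Protocol*

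**What the plan says.** CD4 change from baseline to month 12, where available, is effectiveness outcome (d) in Section 10, under a secondary objective.

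Section 17 treats viral load in two parts. It states "We anticipate most participants will have virological suppression at baseline" and continues "in such participants the proportion of participants with sustained virologic suppression at 6 and 12 months will be described". For the remainder: "For those who are not virologically suppressed at enrolment, changes in viral load will be described".

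The next paragraph covers CD4, renal and lipid data. It begins "Amongst those with available longitudinal CD4 count data" and concludes that "the mean change from baseline in the LA CAB+RPV group and the oral group will be described". It makes no split by baseline suppression, and no other section adds one for CD4.

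On who may be viraemic at baseline:
- One BHIVA criterion listed in Section 7 is "viral suppression for at least 6 months".
- Section 11.2.1 does not hold the LA group to those criteria: "This includes those who have received LA CAB+RPV outside of BHIVA criteria or on compassionate grounds".
- The same section defines the oral group by not being BHIVA-eligible while continuing oral ART. It states no suppression requirement.

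**The concern.** CD4 change over a year means different things in two kinds of participant. In someone who goes from viraemia to control it largely reflects immune recovery. In someone already suppressed it reflects what happens on a change, or continuation, of regimen. A single mean over both describes neither, and because the second kind may change very little, a few large gains can make up much of the mean.

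Section 17 already recognises the two kinds of participant, since it separates them for viral load one paragraph earlier. It also says that the oral group is there to indicate what would have been seen without the switch, so readers will set the two CD4 means next to each other. Those means can differ simply because the groups hold different shares of viraemic people, with no difference between regimens. Restricting the summary to available CD4 pairs could add to this if testing is more frequent in viraemic patients.

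**Working it through.** **No plan figure to reproduce.** The protocol gives no CD4 mean, SD, viraemic share or CD4-testing rate, and no power calculation. The only arithmetic that can be checked is the group sizes: 150 LA participants matched 3:1 gives 150/3 = 50 oral participants, which agrees with Section 17.

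**Inputs**
- From the protocol: n = 150 LA (a minimum) and about 50 oral; most, not all, suppressed at baseline.
- Assumed: viraemic share f = 2% to 15%; mean gain in suppressed participants m_s = 10 cells/µL (range 0 to 20); mean gain in viraemic participants m_v = 150 (range 100 to 200); SD of change 150 (range 100 to 200).

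**Step 1: shift in one group's mean.** Pooled mean = (1 − f)·m_s + f·m_v, so the shift from the suppressed-only mean is f·(m_v − m_s).

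| f | People in 150 | Pooled mean (10 and 150) | Shift | Shift over the assumed ranges |
|---|---|---|---|---|
| 2% | 3 | 12.8 | 2.8 | 1.6 to 4 |
| 5% | 7–8 | 0.95·10 + 0.05·150 = 17.0 | 7.0 | 4 to 10 |
| 10% | 15 | 0.90·10 + 0.10·150 = 24.0 | 14.0 | 8 to 20 |
| 15% | 22–23 | 0.85·10 + 0.15·150 = 31.0 | 21.0 | 12 to 30 |

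At 5% the viraemic participants supply 7.5/17.0 = 44% of the pooled mean.

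**Step 2: compare with sampling error.** SE = SD/√n = 150/√150 = 12.2 (8.2 at SD 100, 16.3 at SD 200). At SD 150 the shift is 7.0/12.2 = 0.57 SE at 5% and 14.0/12.2 = 1.14 SE at 10%. The share needed for a shift of one SE is 12.2/(m_v − m_s): about 12%, 8% or 6% for a difference in gains of 100, 150 or 200.

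**Step 3: selective CD4 availability.** Suppose all viraemic but only half of suppressed participants have paired values (assumed). The viraemic share among pairs is f/(f + 0.5(1 − f)).
- f = 5%: 0.05/0.525 = 9.5%, shift 0.095·140 = 13.3. Pairs number 150·0.525 ≈ 79, so SE = 150/√79 ≈ 16.9.
- f = 10%: 0.10/0.55 = 18.2%, shift 0.182·140 = 25.5. Pairs number 150·0.55 ≈ 82, so SE ≈ 16.6.

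The shift nearly doubles, but the SE also rises because fewer pairs remain.

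**Step 4: difference between the two means.** With the same gains in both groups and no regimen effect, LA minus oral = (f_LA − f_oral)·140.
- LA 5%, oral 0%: +7.
- LA 5%, oral 5%: 0.
- LA 5%, oral 10%: −7.

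The SE of the difference is 150·√(1/150 + 1/50) = 24.5.

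**The case against.** **Detail belongs in the SAP.** Section 17 defers detailed analyses to a statistical analysis plan, and its sentence forbids no stratification, so an SAP could add the split without contradiction. That is true, and it limits the point. Still, Section 17 names the summary to be shown for CD4 and differentiates only viral load, so an author who follows it as written would produce the pooled mean.

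**The viral load split has its own reason.** Sustained suppression is undefined in someone not suppressed at the start, whereas CD4 change is defined for everyone. This stands: the two paragraphs do not contradict each other. The issue is what the CD4 mean represents.

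**Out-of-criteria patients are already to be described.** Section 11.1.1 promises the reasons for ineligibility and the virological and clinical outcomes of LA patients treated outside the criteria. This helps, but it leaves them in the pooled mean and does not cover the oral group. Nor does out-of-criteria mean viraemic: resistance, hepatitis B treatment needs, or BMI and subtype can also place someone outside.

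**A tempting stronger reading.** A reader might infer that viraemic LA starters will inflate the LA mean and make the regimen look better than oral ART. The documents do not support this. They give no viraemic share, the oral group may hold as many viraemic people or more, and Section 17 says that it does not intend to compare the groups formally because their characteristics are expected to differ.

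**Conclusion.** The point holds as a minor reporting weakness in a secondary, descriptive outcome. It is not an error in a formal comparison, because none is planned.

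The pooled CD4 mean in either group can mix two different quantities, and the direction of any resulting difference between groups cannot be known in advance. Its size is conditional on assumed values. With a viraemic share of 2% to 5%, the shift stays below one standard error at SD 150. It reaches one standard error at about 6% to 12%, for a difference in gains of 100 to 200 cells/µL. Selective CD4 testing would enlarge it, but the protocol gives no testing rates.

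The comparison with the standard error shows how visible the shift would be against noise. It does not settle what the mean describes, and recruiting more participants would not separate the two quantities.

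**What to change.** In Section 17, describe CD4 change by baseline suppression within each treatment group, using the split that the section already makes for viral load:
- Show the suppressed-at-baseline figures for LA and oral side by side.
- Report viraemic participants separately, as individual values if there are few.
- In each cell, give the number with paired CD4 values out of the number in the stratum.
- Classify suppression at the individual baseline of Table 1, which for people who started before the site opened is the date of switch.

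The cost is about one sentence in Section 17, carried into the SAP. Table 1 already schedules viral load and, where available, CD4 count at baseline, so no new data are needed. The one drawback is that the viraemic stratum will be small and imprecise.
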